6.0 Statistical Analysis Plan

Statistical Analysis. We will use descriptive statistics to characterize the study participants and survey responses. We will use a one sample t-test to compare the mean SUS score at T₁ to the threshold score of 68 indicative of "above average" usability and a two-sample t-test to compare SUS scores of independent groups (e.g., participants with limited vs. adequate health literacy). If SUS score distributions suggests asymmetry or nonnormality, we will use the one sample median test to compare the median SUS scores at T₁ to the threshold score of 68 and Wilcoxon-Mann-Whitney test to compare the SUS score distributions of two independent groups.

To assess whether there was a significant improvement in the continuous secondary cognitive/behavioral outcomes from baseline to end of study (T₀ to T₁), we will perform two-sided paired t-tests on the pairwise differences. If any of the distributions of pairwise differences suggest asymmetry or nonnormality, the non-parametric Wilcoxon Signed Rank Sum test will be performed in lieu of paired t-tests. We will use the McNemar's test for to compare paired proportions and Fischer's Exact test for independent proportions. All analyses will be completed using statistical software under the supervision of a biostatistician in the Vanderbilt Center for Diabetes Translational Research (CDTR).

Sample Size. In the context of the primary outcome, SUS score, and assuming a standard deviation of 12 based on prior studies, with a sample size of 50, a one sample t-test would detect an absolute difference in mean SUS scores of at least 5 points above the threshold score of 68 with 82% power. Conservatively assuming study dropout of 20%, we aim to enroll 70 participants.

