5.0 Study Procedures

Setting. The Vanderbilt Adult Primary Care (VAPC) clinics and Eskind Diabetes Clinics are located within a large ambulatory care facility in Nashville, TN. An electronic health record (Epic Systems Corp.) stores all clinical data and patients receive access to their clinical data via an integrated and highly-adopted patient web portal, MHAV, that is accessible on desktops and via a native mobile app for iOS and Android mobile operating systems.

Participants and Recruitment. Potential participants will be identified automatically using VUMC's *Subject Locator* to query the EHR for patients with upcoming clinic appointments who meet the discrete inclusion and exclusion criteria. We will send identified patients a letter describing the study. Study flyers will be placed in participating clinic sites. Interested patients will contact a research assistant to learn more about the study and confirm eligibility.

Participants will complete an electronic consent form and enroll online via REDCap. Our target enrollment is 70 participants. In accordance with best practices and to reflect a range of patient experience with diabetes and groups with distinct usability needs, we will recruit a purposive sample to achieve at least 20% representation of each of the following characteristics: (a) limited health literacy and (b) age 65 or over. Some participants may have one or more of these characteristics. Health literacy will be assessed using a validated on one-item screener that asks respondents to rate their confidence independently filling out medical forms. Consistent with prior studies, we will categorize participants noting any lack of confidence filling out medical forms as having limited health literacy.

Data Collection and Outcome Measures. Study participants will complete questionnaires electronically via email using REDCap at two time points: enrollment (T₀) and end of study (T₁). The enrollment questionnaire (T₀) will include basic demographic questions, items about computer/smartphone usage, and validated measures of health literacy and eHealth literacy. Both questionnaires will contain

validated scales to assess study outcomes. Participants will be compensated \$40 for completing the enrollment questionnaire, \$35 for completing the study end questionnaire, and \$5 for first 10 minutes of dashboard use.

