The primary outcome measures will be: (a) ease of use and satisfaction as assessed by the System Usability Scale at T₁, (b) user experience as assessed by end of study questionnaire and semi-structured interviews at T₁. Secondary outcomes will include system usage (total number of dashboard visits, total duration of dashboard use, and use of embedded educational links, secure messaging, and a link to the American Diabetes Association Online Community) and the potential impact of the dashboard on the following secondary cognitive and behavioral outcomes assessed using validated scales at T₀ and T₁: patient activation, diabetes self-efficacy, diabetes knowledge, diabetes care understanding, diabetes self-care, and diabetes distress.

At the conclusion of their one month of dashboard access, we will conduct one-on-one, semi-structured interviews with a subsample of at least 10 participants. This methodology is most appropriate for in-depth assessment of patients' perceptions and reactions regarding a proposed intervention. Interviews are preferred over focus groups for understanding usability because focus groups can amplify bias and individual opinions. Interviews will take place by phone or in person and will last approximately 30 minutes. A trained interviewer will use a semi-structured interview guide to facilitate the interview and elicit in-depth understanding of participants' perceptions and experiences with specific dashboard functionality as well as barriers to use. Additional participants will be enrolled until saturation is reached. Saturation will be defined as no new usability concerns raised in the preceding two interviews and typically occurs between 10 and 30 interviews. Participants will be compensated an additional \$40 for the interview.

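### Does the SUS comparison with 68 need a planned analysis of participants who do not return the end-of-study questionnaire?

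*Combined protocol and SAP*

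**What the plan says.** All references are to the combined protocol and SAP.

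- **Outcome.** Section 5.0 lists as a primary outcome "ease of use and satisfaction as assessed by the System Usability Scale at" T₁. There is no SUS at enrolment, since nobody has used the dashboard by then.
- **Collection.** Section 5.0: "Study participants will complete questionnaires electronically via email using REDCap at two time points", namely enrolment and end of study. Completing the end-of-study questionnaire earns \$35.
- **Test.** Section 6.0: "We will use a one sample t-test to compare the mean SUS score at" T₁ with 68. If the scores look skewed or non-normal, "we will use the one sample median test to compare the median SUS scores at" T₁ with the same value.
- **Sample size.** Section 6.0 states that "with a sample size of 50, a one sample t-test would detect an absolute difference in mean SUS scores" of 5 points or more above 68 with 82% power, taking an SD of 12. It continues: "Conservatively assuming study dropout of 20%, we aim to enroll 70 participants".
- **Related analyses.** Section 6.0 also plans descriptive statistics on participants and survey answers, and a two-sample comparison of SUS between independent groups, with limited versus adequate health literacy as its example.
- **Other data.** The enrolment questionnaire covers demographics, computer and smartphone use, and health and eHealth literacy. System usage ("total number of dashboard visits, total duration of dashboard use" and use of links and messaging) is a secondary outcome.

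The plan defines no analysis set for SUS, gives no rule for missing scores, and does not compare those who return T₁ with those who do not.

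**The concern.** The sponsor expects to lose up to a fifth of participants and uses that expectation only to raise enrolment. Enrolling more people restores precision but leaves any bias from selective return untouched.

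Three features make the question natural here. The comparison is with a fixed external number, so no second arm exists in which similar non-response could cancel. The outcome is how easy an online tool is to use, and it is collected by an online questionnaire, so people who struggle with the tool might also be less likely to answer. And section 5.0 refers to "groups with distinct usability needs, we will recruit a purposive sample to achieve at least 20% representation" of limited health literacy and of age 65 or over, so uneven return could thin out the groups the study set out to include.

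The value 68 is the plan's only numerical benchmark for usability, and section 2.0 places the study ahead of a larger trial. If non-responders would have scored lower, a statement that usability is above average might hold for responders and not for everyone enrolled.

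**Working it through.** **Inputs.** From section 6.0: benchmark 68, difference 5 (mean 73), SD 12, 50 evaluable, 82% power, 20% dropout, 70 enrolled. Assumed: two-sided alpha 0.05, which the plan does not state for this test, and d, the responder mean minus the mean non-responders would have given. The documents offer no value for d.

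**1. The plan's own figure.** The noncentrality is 5 / (12/√50) = 2.946 on 49 degrees of freedom. The noncentral t gives 82.3%, matching the stated 82%.

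**2. Does the allowance protect power?** 70 × 0.80 = 56 responders, with power 86.5% at a mean of 73. With 63 responders it is 90.2%. Only 50 / 0.80 = 62.5, so 63, need be enrolled. Enrolling 70 tolerates a loss of 20/70 = 28.6% before the evaluable number falls below 50. Power is not at issue.

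**3. Size of a possible bias.** With missing share m, enrolled mean = responder mean − m × d, so the overstatement is m × d. For d = 5, 10 and 15 this is 1, 2 and 3 points at m = 20%, and 0.5, 1 and 1.5 points at m = 10%.

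**4. Gap needed to bring the mean to 68.** With responder mean M, d = (M − 68)/m. At M = 73:
- m = 20%: 5/0.20 = 25
- m = 10%: 5/0.10 = 50
- m = 28.6%: 5/0.286 = 17.5

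**5. Gap needed to bring the lower 95% limit to 68.** Two targets must be kept apart.

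(a) *The gap at which the planned t-test would lose significance.* This uses the full half-width h = t(0.975, n−1) × 12/√n, and d = (M − 68 − h)/m.

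(b) *The limit for the mean of the 70 people enrolled.* This is the relevant target, because the sample is purposive and no wider population is claimed. The n returned scores are known, so only the missing ones add uncertainty. For fixed d, the error variance is m² × 12² × (1/n + 1/(70 − n)) = m × 12²/n, so the half-width is h × √m. At n = 56 the SE is 1.604 × √0.20 = 0.717 and the half-width is 3.21 × 0.447 = 1.44.

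| Responders | m | h | d, target (a), M = 73 | h√m | d, target (b), M = 73 |
|---|---|---|---|---|---|
| 63 | 10% | 3.02 | 19.8 | 0.96 | 40.4 |
| 56 | 20% | 3.21 | 8.9 | 1.44 | 17.8 |
| 50 | 28.6% | 3.41 | 5.6 | 1.82 | 11.1 |

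For the people actually enrolled, the result withstands about twice the gap that the full standard error suggests. At M = 72 and 20% missing, (a) gives (4 − 3.21)/0.20 = 3.9 and (b) gives (4 − 1.44)/0.20 = 12.8.

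**6. What a planned analysis would add.** Every quantity in steps 4 and 5 follows from M, the SD, n and the number enrolled. The one unknown, d, stays unknown whether or not a tipping-point analysis is written into the plan.

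**The case for a change.** The strongest argument for a change is that selective return can inflate the chance of a favourable finding while the planned analysis shows nothing. Suppose the true mean of everyone enrolled is exactly 68 and 56 respond. The chance of a significant result above 68, nominally 2.5%, becomes about 9%, 23% and 45% for d = 5, 10 and 15. A weaker result is also more exposed: at a responder mean of 72 with 20% missing, a gap of 3.9 points would remove the t-test's significance. The remedy would take a paragraph, and writing it before T₁ data are seen avoids any appearance of selection.

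Part of this stands. The plan has no non-response analysis, and the SUS result describes T₁ responders. The planned comparison by health literacy would show whether one of the targeted groups rates the dashboard differently, and the planned descriptives characterise participants. Both narrow the gap, but neither compares responders with non-responders. The interviews need not include people who failed to return T₁.

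The rest does not carry a change. Each inflated error rate depends on an assumed d, and the full-SE gaps of 3.9, 5.6 and 8.9 are not limits for the mean of the enrolled. The 28.6% loss exceeds what the plan, by its own description conservatively, assumes. Payment for the T₁ questionnaire and a follow-up of one month also favour return. A tipping-point analysis with no threshold for d would leave the reader with the same judgement to make. Applied alongside the median fallback, a mean-based version would not test the conclusion being reported.

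**Conclusion.** The observation is accurate, but no change to the plan follows. Carried out as written, the plan gives a sound comparison with 68 for participants who return T₁, with 82% power at 50 responders and 86.5% at the expected 56. In the plan's own scenario (SD 12, responder mean 73, 20% missing), non-responders would have to score 25 points lower for the enrolled mean to reach 68, or about 17.8 points lower for its lower 95% limit to do so. These figures assume two-sided alpha 0.05 and a fixed gap d, for which the documents provide neither a value nor evidence.

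No stop-or-proceed rule in section 2.0 depends on 68. User experience is also a primary outcome and is assessed separately by questionnaire and interview, so no decision changes on this point. Competent reporting fills the gap: give the T₁ response rate, word the SUS result as applying to responders, and describe non-responders on whatever enrolment and usage data are available. None of that needs an amendment, and none of it would alter the primary test, the sample size or the data collected.

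### Does leaving the significance level and sidedness of the primary SUS test unstated leave its decision rule open?

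*Combined protocol and SAP*

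**What the plan says.** Section 6.0, under Statistical Analysis, sets out the primary quantitative test: "We will use a one sample t-test to compare the mean SUS score at T₁ to the threshold score of 68". If the scores look skewed or non-normal, a one-sample median test replaces it. Neither test is given a significance level or a sidedness, and no significance level appears anywhere else in the document. Sidedness is mentioned once, in the next paragraph, for the secondary cognitive and behavioural outcomes: "we will perform two-sided paired t-tests on the pairwise differences".

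Under Sample Size, the same section gives the inputs, "assuming a standard deviation of 12 based on prior studies" and 50 evaluable participants, and the result, that the test "would detect an absolute difference in mean SUS scores of at least 5 points above the threshold score of 68 with 82% power". It closes with "Conservatively assuming study dropout of 20%, we aim to enroll 70 participants". Section 5.0 repeats the target of 70.

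**The concern.** A power statement has four inputs besides the choice of test: sample size, effect, SD and significance level. This one gives three. The authors also wrote the sidedness for the secondary outcomes and left it out for the primary one. The power sentence speaks of a difference above 68, so a reader could take the primary test to be one-sided at 0.05.

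If the rule were truly open, it could be chosen after the data were seen. A result that falls short at two-sided 0.05 might pass at one-sided 0.05. With a true mean of 68, the chance of wrongly claiming better-than-average usability would be 5% rather than 2.5%. The enrolment step also looks odd at first, because a 20% allowance on 50 does not give 70.

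**Working it through.** **Inputs.** All are from section 6.0: threshold 68, difference 5, SD 12, evaluable n = 50, stated power 82%, dropout 20%, enrolment 70. The significance level is an assumption in every run, because the document gives none.

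**1. Reproduce the 82%.** The noncentrality is (5/12) × √50 = 2.946 on 49 degrees of freedom. Exact power from the noncentral t distribution is:

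| Assumed level | Power at n = 50 |
|---|---|
| two-sided 0.05 | 82.3% |
| one-sided 0.025 | 82.3% |
| one-sided 0.05 (or two-sided 0.10) | 89.6% |
| two-sided 0.025 | 73.5% |
| one-sided 0.01 | 70.5% |
| two-sided 0.01 | 60.7% |

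Solving backwards, exactly 82% corresponds to a two-sided level of 0.0486, and any power that rounds to 82% corresponds to about 0.047 to 0.051. Two-sided 0.05, or its one-sided 0.025 equivalent, is the only conventional level that fits. As a further check, one-sided 0.05 would reach 82% with 40 participants, whereas two-sided 0.05 first reaches it at 50, which is the plan's number.

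**2. Do the two fitting levels differ in practice?** For an upward claim they do not. Both reject when the mean exceeds 68 + t(0.975) × 12/√n. At n = 50 this is 68 + 2.010 × 1.697 = 71.41. At n = 56 it is 68 + 2.004 × 1.604 = 71.21.

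**3. What would one-sided 0.05 change?** The critical mean would be 68 + 1.677 × 1.697 = 70.85 at n = 50, and 68 + 1.673 × 1.604 = 70.68 at n = 56. At n = 56 the two rules disagree only for an observed mean between 70.68 and 71.21 (at SD 12), a band of 0.53 points. For example, a mean of 71.0 gives t = 3/1.604 = 1.871, with p = 0.067 two-sided and 0.033 one-sided. The chance of disagreement is the difference between the two powers:

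| True mean (n = 56) | One-sided 0.05 | Two-sided 0.05 | Difference |
|---|---|---|---|
| 71 | 58.0% | 45.2% | 12.9% |
| 73 (planned) | 92.4% | 86.5% | 5.9% |
| 75 | 99.6% | 99.0% | 0.6% |

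(Differences are taken before rounding.)

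**4. Enrolment.** 50/(1 − 0.20) = 62.5, so 63 are needed. Enrolling 70 with 20% dropout leaves 70 × 0.80 = 56, with 86.5% power at two-sided 0.05. Fifty evaluable remain until dropout reaches 1 − 50/70 = 28.6%.

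**The case for a change.** The strongest reply is that a decision rule should be read from the plan, not worked back from a power figure. The plan chose a formal test with a power calculation for a primary outcome, and a power statement without a level is incomplete. The directional wording, set beside an explicit two-sided label on the secondary tests alone, could suggest that the primary test was meant to differ. The median-test fallback has no stated level either.

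The omission is real, and that part of the reply stands. The claimed ambiguity is weaker. The secondary paragraph of section 6.0 asks about improvement, which is just as directional, and uses two-sided tests. The plan's own practice is thus to pair a directional aim with a two-sided test. The sentence describing the primary test carries no direction, and the power sentence describes the alternative of interest, not the rejection region. Above all, one-sided 0.05 contradicts the stated 82%. Back-calculation cannot separate two-sided 0.05 from one-sided 0.025, but for an upward claim that distinction has no effect. The fallback replaces the same comparison, so the same level carries over to it.

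**Conclusion.** No change follows. The 82% is correct at 82.3%, and it identifies the level: two-sided 0.05, or equivalently one-sided 0.025 for an upward claim. The cut-off can therefore be recovered from the plan before any data are seen. This is missing detail that a competent analyst fills in one sensible way. It is not an arithmetic error or an open choice.

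The consequence of a misreading is also limited. It would matter only for an observed mean within about half a point, against a planned difference of 5, and at the planned true mean of 73 that has a 5.9% chance. The 12.9% figure needs a true mean of 71, short of the planned alternative. Sections 2.0 and 7.0 present the work as a usability study ahead of a larger trial, with interviews used to guide revisions. No stated decision depends on the SUS p-value.

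The step from 50 to 70 is a cautious margin over the 63 required, in keeping with the plan's own description of its allowance as conservative.

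These conclusions assume SD 12, roughly normal SUS scores, 56 completers where that figure is used, and that the authors worked from a conventional significance level.

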7.0 Qualitative Analysis Plan

We will transcribe participants' semi-structured interviews for coding and analysis of user experience. We will use selective coding to identify participants' statements addressing six established elements of user experience (i.e., the core category): (1) useful - fulfilling a need, (2) useable - ease of use, (3) accessible - easy to access and comprehend, (4) desirable - design elements that evoke emotion or appreciation, (5) findable - easy to navigate, and (6) credible - trustworthy and believable. Two research assistants will independently code all interviews then resolved any differences by consensus. We will review participant statements in each category for inform potential revisions that could improve user experience with the dashboard.
